6.4. Point of enrolment

A subject is considered enrolled in the investigation when the written informed consent is obtained. The expected duration for each subject is described in section 4.1.

6.5. Total expected duration of the clinical investigation

The dates below are approximate, and no subjects will be enrolled before required approval has been obtained.

- First subject enrolled (09/2020).
- Last subject enrolled (11/2020).
- Last subject completed (12/2020).
- Final report (12/2021).

7. Procedures

7.1. Clinical investigation-related procedures

Before initiation of the clinical investigation, sponsor must be provided with key personnel signed and dated curriculum vitae (not more than 2 years old) to verify their qualifications. Key site personnel are those, who treat or evaluate subject data in the clinical investigation. Also, the sponsor will ensure that all site personnel

are trained in the investigation procedures, how to complete the CRFs, procedure for reporting an adverse event or serious adverse event (how, when, to whom), and who to contact in case of emergency related to the investigational device.

See section 7.3 Flow-charts for a more detailed overview of the clinical investigation-related procedures at visits, phone visits and at product/baseplate change.

7.1.1. Visits

Visit 0 (Inclusion visit)

If a potential subject is interested in participating after the first contact, a visit (visit 0) will be arranged at subject's home or at a clinic or at Coloplast, if subjects prefer not to have visits in own home, in a room reserved to ensure privacy and quiet surroundings. When arranging the visit, it will be ensured, that the subject has received the Subject Information Form prior to the visit. The subjects will receive both written and verbal information to ensure that the subject understands what was read and explained and can freely agree to participate in the investigation. The subject will, beforehand, also be informed about the possibility of bringing a companion to Visit 0 and to any possible subsequent visits. During the visit the principal Investigator, or delegate, will provide oral information about the investigation based on the Subject Information Form. The subject has the right to wait before deciding on participation.

If/when subjects decide to participate, they will be asked to sign the Informed Consent Signature Form. If a subject so desires, and it is certain that it is understood what the investigation entails, and the relevant form has been signed, the subjects are considered enrolled in the investigation. Enrolled subjects that are deemed eligible per the inclusion/exclusion criteria are allocated a subject number. Visit 0 and visit 1 can be combined.

Visits 1 (V1)

During visit 1, part 1 of the questionnaire Table 1 (demographic questions) will be completed by the Principal Investigator, or delegate. The subject will be trained in the use of the test product per IFU. The subjects are instructed to continue their everyday life and change test product whenever they feel the need to.

Visits 2 (V2)

During visit 2, the Principal Investigator, or delegate will ensure part 2 of the questionnaire [Table 2](#) will be completed by subjects. Potential (S)AE's will be captured by the Principal Investigator, or delegate. Hereafter termination If appropriate, subjects may be interviewed regarding use of the test product by a Coloplast representative at V2, otherwise an alternative time for interview may be scheduled.

7.2. Activities performed by sponsor representatives

Sponsor (Clinical Manager or a representative hereof) is responsible for:

1. Training of investigator and study personnel in the informed consent procedure, study procedures,
 - a. how to use the products, complete the CRF, how to report possible safety issues and in ISO 14155.
 - b. All training will be documented by site
2. Support during the recruitment process and conduct of the investigation
3. Monitoring

7.3. Flow-charts

Table 1: chart showing the connection between visits and assessments

Assessment	Type of assessment	Assessed by	V0/V1	V2
General				
Oral information		Investigator	X	
Written informed consent	Informed Consent Form	Subject	X	
Consent to interview	Informed Consent Form - Interview	Subject	X	
Check of inclusion and exclusion criteria	CRF	Investigator	X	
Subject number allocated		Investigator	X	
Assessment	Type of assessment	Assessed by	V0/V1	V2
Demographics	Part 1 questionnaire	Investigator	X	

 Age Level of incontinence (how often, how much) Usual product/management routine (using a product, what type, how many) Reason for incontinence (if known) Duration of incontinence (for how long have subject had current issues) 				
Endpoint assessment:	Part 2 questionnaire (Table 2)	Subject		X

 Comfortability Handling Subject experience of use 				

CONFIDENTIAL

Page 17 of 34

Registration of AEs/SAEs	AE/SAE form	Investigator	X
Termination	Termination form	Investigator	X

Table 2 chart showing the connection between visits and endpoints.

Assessment	Type of assessment	Assessed by	V0/V1	V2	Derived from
Endpoint	Questions UK				Answers UK
Frequency of success in support of "comfortable"	How comfortable was the product to wear?	Subject		X	Very uncomfortable – uncomfortable – neither uncomfortable nor comfortable – comfortable – very comfortable
Frequency of success in support of "easy to apply"	How was the product to apply?	Subject		X	Very difficult – difficult – neither difficult nor easy – easy – very easy
Frequency of success in support of "easy to remove".	How was the product to remove?	Subject		X	Very difficult – difficult – neither difficult nor easy – easy – very easy
Frequency of success in support of "easy to urinate during wear".	How was it to urinate normally while wearing the product?	Subject		X	Very difficult – difficult – neither difficult nor easy – easy – very easy

CONFIDENTIAL

Page 18 of 34

Frequency of success in support of "no product awareness during wear"	While wearing the product, how aware were you of wearing it?	Subject	Subject	X	Noticed all the time – noticed some of the time – Don't know – didn't notice much – didn't notice at all
Frequency of success in support of "easy to open/close functionality"	How was it to use the open/close functionality at the front of the product?	Subject	Subject	X	Very difficult – difficult – neither difficult nor easy – easy – very easy
Frequency of success in support of "feeling secure"	How was your feeling of security while wearing the product?	Subject	Subject	X	Very poor – poor – neither poor nor good – good – very good
Frequency of success in support of "discreetness during wear"	How discreet did you find the product during wear?	Subject	Subject	X	Very indiscreet – indiscreet – Don't know – discreet – very discreet
Frequency of success in support of "discreetness during urinating using the opening"	How discreet did you find the product when you needed to urinate by using the opening at the front?	Subject	Subject	X	Very indiscreet – indiscreet – Don't know – discreet – very discreet
Frequency of success in support of "discreetness in the level of urine smell"	How discreet did you find the smell of urine from product?	Subject	Subject	X	Very indiscreet – indiscreet – Don't know – discreet – very discreet

CONFIDENTIAL

Page 19 of 34

	How discreet did you find the noise from product, while you were wearing it?	Subject	X	Very indiscreet – indiscreet – Don't know – discreet – very discreet
Frequency of success in support of "discreetness in the level of noise"	To what extend do you agree in the following statement: The product supports me in living the life I want	Subject	X	Strongly disagree – disagree – Don't know – agree – strongly agree
Frequency of success in support of "living the life you want"	How confident were you that you could manage your incontinence while wearing the product?	Subject	X	Very insecure – insecure – Don't know – confident – very confident
Frequency of success in support of "the feel of confident management"	Did the product give you a dry feeling?	Subject	X	Not at all – no – Don't know – yes – yes very much
Frequency of success in support of "a dry feeling"	Did the flex collar provide a good fit?	Subject	X	Not at all – no – To some degree – yes – yes very much
Frequency of success in support of "a good fit – flex collar"	Did the whole product provide a good fit?	Subject	X	Not at all – no – To some degree – yes – yes very much
Frequency of success in support of "a good fit – whole product"				

CONFIDENTIAL

Page 20 of 34

Frequency of success in support of "stays in place"	Did the product stay in place during use?	Subject	X	Not at all – no – Don't know – yes – yes very much
Frequency of answers pertaining to yes in support of "future use"	If, possible, would you want to use the product in the future?	Subject	X	Yes - No
Frequency of answers pertaining to yes in support of "reliability for in-home use"	Do you rely on the product being functional for use at home?	Subject	X	Yes - No
Frequency of answers pertaining to yes in support of "reliability for use away from home"	Do you rely on the product being functional for using away from home? By this we mean e.g. at work, during sports, being social or when traveling.	Subject	X	Yes - No
Frequency of answers pertaining to yes in support of "future recommendation"	Would you recommend the product to others?	Subject	X	Yes - No
Frequency of answers pertaining to yes in support of "preference"	Do you prefer this product over your normal product / normal management routine?	Subject	X	Yes - No

CONFIDENTIAL

Page 21 of 34

Additional assessments				
What size product did you use	Subject	X		Large – Regular - both
If both – which size did you prefer	Subject	X		Large - Regular
How many products did you typically use per day? (categories)	Subject	X	• 1 • 2 to 3 • 4 to 5 • 6 or more	
In average, for how long did you typically use one product? (categories)	Subject	X	• 1-2 hours • 3-4 hours • 5-6 hours • 7-12 hours • More than 12 hours	
Where did you use the products? (categories, more answers are allowed)	Subject	X	• At home • At work • At social event(s) • While doing sports • During travel/trip • At night	
Did you experience leakage? (Y/N)	Subject	X	Yes - No	
If yes – when? (categories, more answers are allowed)	Subject	X	• While sitting • While standing • While moving about • While laying down Other, please describe _____	

CONFIDENTIAL

Page 22 of 34

If yes – how often? (categories, more answers are allowed)	Subject	X	• Several times a day • Once a day • 5-6 times during the week • 2-4 times during the week • 1 during the week

CONFIDENTIAL

Page 23 of 34

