6.1. Inclusion and exclusion criteria

To be included in the investigation, the subjects must comply with the selection criteria described below

Inclusion criteria:	Justification:

1. Have given written informed consent2. Male3. Be at least 18 years of age and have full legal capacity4. Suffering from urinary incontinence equivalent to using up to 6 pads or 2 diapers per day5. Have had current incontinence issues for at least 3 months6. Able to understand patient information and able to change the product himself7. Up to 6 of the subjects can be users who are using an intermittent catheter due to retention, but who are also dribble incontinent in-between catheterizations, and hence need a product to handle the incontinence.8. Able to fit the test product.	
1. To meet the Helsinki Declaration2. To meet the target population of this device3. To meet the Helsinki Declaration4. To meet the target population of this device5. To be sure subjects meets target population of this device6. To meet the Helsinki Declaration7. To meet the target population of this device8. To meet the target population of this device

CONFIDENTIAL

Page 13 of 34

Exclusion criteria:	Justification:

 1. If experiencing incontinence less than once per week 2. Bedridden, using wheelchair or using a walking aids regularly 	
 1. To meet the target population of this device 2. To meet the target population of this device

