6.2. Recruitment and enrolment

Recruitment of potential subjects will begin once approval has been obtained from Ethics Committee.

Recruitment method	Coloplast Database	Advertisement	Patient records
Potential subjects	
Recruitment will go through Coloplast own subject database (Intermittent Catheterization users) in Denmark. Potential subjects are identified by the following searching criteria in the Coloplast database:
 
 • Has consented to be contacted regarding clinical investigations • Using Intermittent Catheterization • Male • Be at least 18 years of age 	
Advertisement i.e. in local shops, sports facilities, local newspapers, social media and patient associations. The advertisement will state the contact info of investigator or delegated study personnel to contact. A CRO may help by receiving reply letters-mails and/or answering the phone from interested subjects.
	
Recruitment from hospitals, home care nurses and outpatient urology clinics will be via patient visit or screening of subject records kept at the participating sites. Only contact information regarding potential subjects who are assessed eligible will be passed on.

First contact	The identified potential subjects will as first contact be sent an Invitation and Reply Letter by mail or email.	Interested subject contact the investigator or delegated study personnel	The identified potential subjects will be contacted and informed about the investigation by the investigator or delegated study personnel (First contact will be by letter or email, a follow-up contact can be via telephone, letter or email).
	If a potential subject does not return the reply letter or answer the email, they may be contacted by phone, mail or email to make sure that they have received the approach.		
Second contact	
If potential subjects return the Reply Letter/reply to the email, or have called the investigator as first contact and are interested, the Investigator or delegated site personnel will contact the subjects by phone and give a short introduction to the investigation and go over the inclusion and exclusion criteria.
 
If the subjects do not meet the inclusion criteria or meet the exclusion criteria, this will be registered in the Subject Screening Log.
		

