7.6. Supplementary materials and equipment (if applicable)

The Sponsor will provide the Principal Investigator, or delegate with supplementary materials for this investigation. Supplementary materials would be:

- Computer or Iphone with access to eCRFs
- Nurse kits including disposal bags, gloves, gauze, disinfection gel etc.

8. Monitoring and source data verification

All data collected will be directly entered into the eCRF and the EDC system will via edit checks ensure that all fields are completed in the eCRF.

The Informed Consent Forms and (S)AE/ADE will be 100% monitored for timely completeness. eCRF's will be remotely monitored with regards to completeness.

Only the investigator, delegated site personnel and the sponsor representatives will have access to all the eCRFs. The subject will have access to his/her own CRF.

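### Three secondary claims presuppose urinating while wearing the product or using its front opening, but Table 2 gives men without that experience no way to say so

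*Combined protocol and SAP*

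**What the plan says.** Three secondary claims in section 7.3, Table 2 rest on these questions:

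1. Ease of urinating during wear: "How was it to urinate normally while wearing the product". The middle answer is neutral.
2. Ease of the open/close function: "How was it to use the open/close functionality at the front of the product". The middle answer is neutral.
3. Discreetness when urinating through the opening: "How discreet did you find the product when you needed to urinate by using the opening at the front". The middle answer is 'Don't know'.

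None offers a did-not-use answer, and no Table 2 question asks whether the man urinated while wearing the product or used the opening. Elsewhere the table does use conditional items, for example "If both – which size did you prefer".

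Section 9.1 defines success on a 5-point item as the two best categories and bases percentages on non-missing data. Sections 9.1 and 9.4 let a claim pass when the lower 95% confidence limit exceeds 50%. Section 8 states that "the EDC system will via edit checks ensure that all fields are completed in the eCRF".

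On who might lack the experience, section 6.1 allows: "Up to 6 of the subjects can be users who are using an intermittent catheter due to retention". One of the three recruitment routes in section 6.2 targets such men: "Recruitment will go through Coloplast own subject database (Intermittent Catheterization users) in Denmark". At V1 (section 7.1.1), "The subject will be trained in the use of the test product per IFU". The men are then told to carry on with everyday life, and the visit text does not require them to use the opening.

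**The concern.** A man who removed the product to urinate, or never used the opening, cannot answer these questions from experience. His score then depends on how he fills the gap. A middle answer is a non-success that stays in the denominator. A guessed favourable answer is a success. A blank would leave the denominator, but whether a blank is possible is unclear: section 8 says all fields are completed, yet Table 2 contains conditional items that some men must skip.

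Each claim passes or fails on its own, and the secondary objective is to support commercial claims. With about 20 men, a few such answers can decide a result in either direction, and the data would not show that this had happened.

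**Working it through.** **Inputs from the plan.** 20 subjects (section 9.2); exact binomial analysis against 50% with two-sided alpha 0.05 (9.1); pass if the lower 95% limit exceeds 50% (9.4). The plan states no power, so there is no figure of its own to reproduce.

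**Assumptions, not in the documents.** All 20 men are evaluable; k of them lack the experience; the true success rate p among users is 80, 85 or 90%; non-use is unrelated to the product.

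**Step 1: the threshold.** The exact (Clopper-Pearson) lower limit for x successes in n is the 2.5% quantile of Beta(x, n−x+1). For n=20, 15/20 gives 50.9% (pass) and 14/20 gives 45.7% (fail), so 15 successes are needed. The smallest passing counts for smaller n are 15/19, 14/18, 13/16 and 12/14 (57.2%; 11/14 gives 49.2% and fails).

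**Step 2: non-users give the middle answer.** Users must then supply all 15 successes.

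- Counted as non-successes: P(X ≥ 15), X ~ Bin(20−k, p).
- Excluded: P(X ≥ r), X ~ Bin(20−k, p), with r the threshold for n=20−k.

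Pass probability, counted versus excluded:

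| k | r of n if excluded | p=80% | p=85% | p=90% |
|---|---|---|---|---|
| 0 | 15/20 | 80.4% (same) | 93.3% (same) | 98.9% (same) |
| 1 | 15/19 | 67.3% (same) | 85.6% (same) | 96.5% (same) |
| 2 | 14/18 | 50.1 vs 71.6% | 72.0 vs 87.9% | 90.2 vs 97.2% |
| 4 | 13/16 | 14.1 vs 59.8% | 28.4 vs 79.0% | 51.5 vs 93.2% |
| 6 | 12/14 | 0 vs 44.8% | 0 vs 64.8% | 0 vs 84.2% |

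At k=6 the best possible result is 14/20, which fails.

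For a given k these gaps are the most that the choice of denominator can make. They apply if the users-only rate decides the claim and vanish if the all-subjects rate does.

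**Step 3: non-users guess at random over five categories (40% success).** P(pass) = Σ_j Bin(j; k, 0.4) × P(X ≥ 15−j), X ~ Bin(20−k, p). For k=2, 4, 6 this gives 66, 49, 33% at p=80%, and 95, 84, 63% at p=90%.

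**Step 4: non-users all answer favourably and the feature is no better than 50%.** P(X ≥ 15−k), X ~ Bin(20−k, 0.5), gives 4.8, 10.5 and 21.2% for k=2, 4, 6. With 20 real users it is P(X ≥ 15), X ~ Bin(20, 0.5) = 2.1%.

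**Step 5: what exclusion does.** At a true 50%, the users-only rule passes with probability 1.5, 1.1 and 0.6% for n=18, 16, 14, so it does not inflate false passes when non-use is unrelated to the product. It can flatter the product when men avoid the opening because they dislike it. If 5 avoid it and 13 of 15 users succeed, the users-only lower limit is 59.5% (pass), while 13/20 gives 40.8% (fail).

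**The case against.** **The size rests on an unknown k.** This stands. No passage gives the number of non-users, and at k=1 the choice of denominator makes no difference. A reader might infer that six catheter users cannot answer and that the claims are bound to fail. The documents do not support that: six is a cap, and nothing says whether these men urinate while wearing the product or use its opening. Catheter use says least about the open/close item, since every man is trained, although training does not show use during the week. The problem also does not depend on catheter users, because any man may remove the product to urinate.

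**Section 9.1 allows data points to be excluded.** It does, but its example is protocol violations and it does not name non-use. The interviews in section 7.1.1 cover use of the product, so some information may exist. They are optional and not an endpoint source, so they cannot identify non-users systematically.

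**The third item already offers 'Don't know', and counting non-users as non-success is a defensible conservative rule.** Both are fair. For that item the difficulty is mainly scoring, and the all-subjects rate is a legitimate choice. But the plan does not say it has made that choice, and a favourable guess is not conservative.

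**The fielded eCRF may contain skip logic.** Possibly; it is not in the documents.

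**The boundary of three items is arbitrary.** Partly right. Reliance on the product away from home is a forced yes/no, and men who used it only at home may face a similar gap. That one can be checked from the Table 2 question on where the products were used.

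**Conclusion.** The point holds as a minor one. As written, the three claims can be moved up or down by men who lack the experience asked about, and no planned questionnaire item identifies them. Under the assumptions above (20 evaluable men, non-use unrelated to the product), the effect ranges from no difference between the two denominators at k=1 to a claim that cannot pass at k=6 if all six give the middle answer. If non-users all answer favourably, the chance of passing a 50% feature rises from 2.1% to as much as 21%.

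A reader might infer that the plan is biased against the product. The documents do not support a direction, because it depends on how non-users answer. The primary endpoint on comfort is unaffected, and the study is exploratory.

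**What to change.** **Questionnaire.** Add an item-specific answer and allow it in the edit checks:

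- item 1: 'Did not urinate while wearing the product';
- item 2: 'Did not use the open/close function';
- item 3: 'Did not urinate using the opening'.

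The wording should follow each question. Section 5.1 describes the opening as the route for urinating during wear, so an option about urinating in the product could be ticked by a man who used the opening as intended.

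**Section 9.1.** State now which rate decides each claim. The data review meeting is too late for this, since the study is open-label and sponsor staff may see the data beforehand. Report side by side the rate among men with the experience, the number without it, and the all-subjects rate with non-users as non-success.

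**Men who have already completed the questionnaire.** No users-only rate exists for them. Report the all-subjects rate, show it with and without catheter users (from the Part 1 management routine), and state in the report that non-users could not be identified. The catheter split is a rough display only: it drops catheter users who did use the opening and keeps other men who did not.

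**Cost.** The new answers change an assessment method, so section 11 calls for a CIP amendment. On the approximate dates given (last subject enrolled 11/2020, a test period of one week plus up to three days, plan dated 1 December 2020) it may reach few or no men. The catheter display needs no amendment, because 9.1 allows other summaries. The users-only rate rests on fewer men (12/14 needed if six are excluded) and is biased upward if men avoided the opening because they disliked it, which is why both rates should be shown.

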9.1. Statistical design, method and analytical procedures

Endpoints and assessments

All baseline assessments, endpoints and other measurements will be reported by descriptive statistics and/or listed.

Analysis populations

Intention to Treat (ITT), Safety and Per Protocol (PP) populations will be defined at a formal data review meeting just before database lock. As a minimum, the clinical manager and the statistician will be involved in the classification of subjects.

The Safety population (basis for the AE summary) will constitute subjects with valid informed consent.

The ITT population (Full analysis set) will constitute all subjects, with valid informed consent, who have been exposed to at least one product and furthermore, with information recorded on at least one endpoint (non-missing).

No formal PP population is planned. However, if additional explorative analyses are deemed necessary, a PP population will be established, based on a subset of the ITT population.

Individual endpoints/data points may be excluded from analysis, even though the corresponding subject belongs to the ITT population. This situation could arise due to protocol violations, where, at one visit, the primary endpoint could be affected, but same effect did not occur at the following visit.

All analysis will be based upon the ITT population and AEs will be summarized based on the safety population.

Any exclusion of subjects or data points from any of the populations must be documented.

Descriptive statistics for continuous variables are presented with N, Mean, SD (standard deviation), Median, Min and Max), where N denotes the number of subjects contributing with non-missing data. For discrete variables, descriptive statistics are presented with N and percentage, where percentage is based on the total number of subjects/observations with non-missing data.

A significance level of alpha equal to 0.05 (two-sided) is applied.

All endpoints will be analyzed by an exact test in the binomial distribution (proportion is equal to 50%), where the frequency of success or will estimated with 95% confidence limits.

The two highest or best categories in questions obtained from a 5-point ordinal scale is defined as a success. Likewise, the answer yes, is defined a success, obtained from questions with a yes/no categorical option.

In favor of a claim, the lower 95% confidence limit must be above 50%.

Other summaries and analyses can be made, if relevant.

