9.4. Pass/fail criteria

The study is conducted as a proof of concept study.

Pass criteria is defined as: In favor of a claim, the lower 95% confidence limit must be above 50%.

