10.3. Data retention

The sponsor file will be archived for a minimum period of 10 years after the final clinical investigation report has been signed.

All investigation site documents will be archived for a minimum period of 10 years after the final clinical investigation report has been signed.

11. Amendments to the CIP

Any significant changes to the CIP are:

- Agreed between sponsor and PI
- Justified in a statement included in the amended section and the version number and date of amendment must be documented
- Registered in the Change Log
- Notified to or approved by the EC before implementation
- Notified to or approved by the regulatory authorities before implementation

Example of significant change: Changes of inclusion criteria, end points or assessment methods.

12. Deviations from Clinical Investigation Plan

The Investigator is not allowed to deviate from the CIP unless under emergency circumstances and to protect the rights, safety and well-being of the subject(s). Deviations must be reported to sponsor and deviations affecting the scientific aspect of the investigation or the safety of the subject are reported to the EC by sponsor if required.

In case of continued or repeated deviations affecting the scientific aspect of the investigation or the subjects' rights, safety and well-being sponsor will disqualify the Investigator from further participation in the investigation.

13. Device Accountability

All access to the investigational devices used in the clinical investigation is controlled by storage procedures and device accountability logs as described below. The investigational devices must only be used in this clinical investigation and only per this CIP.

Sponsor keeps a device accountability log that states the physical location of all investigational devices from shipment of investigations devices to the investigational sites until return of or disposal.

The Investigator or an authorized designee keeps records documenting the receipt, use and return and disposal of the investigational devices, which includes:

- Date of receipt
- Identification of each investigational device (batch no./serial no./unique code) and number received
- Number of devices used
- Subject identification
- Identification of each investigational device (batch no./serial no./unique code) and number returned
- Date of returned investigational device

14. Statement of compliance

The clinical investigation is conducted in accordance to:

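### A pass on the 'no product awareness' item can rest on men who noticed the product a little, so it does not by itself support the claim as worded

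*Combined protocol and SAP*

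**What the plan says.** Table 2 in section 7.3 gives the endpoint as frequency of success in support of "no product awareness during wear". The question, answered by the subject at V2, is "While wearing the product, how aware were you of wearing it", and the scale runs "Noticed all the time – noticed some of the time – Don't know – didn't notice much – didn't notice at all".

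Section 9.1 sets one scoring rule for all such items: "The two highest or best categories in questions obtained from a 5-point ordinal scale is defined as a success". It makes no exception for the awareness item. Each endpoint is tested with an exact binomial test against 50%, two-sided at 0.05, with 95% confidence limits. Section 9.4 states the decision rule: "Pass criteria is defined as: In favor of a claim, the lower 95% confidence limit must be above 50" per cent.

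The secondary objective in section 3.1 is to support commercial claims. Section 9.2 sets 20 subjects without a formal calculation, and drop-outs are not replaced.

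**The concern.** The scale separates low awareness from no awareness by giving each its own answer. The success rule then merges them, and the merged count is credited to a claim of no awareness. A man who picks the second-best answer has said that he noticed the product a little, although the answer for not noticing it was open to him.

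This is not an objection to top-two scoring in general. In the other 16 five-point items the second-best answer carries the claimed property: the product is comfortable, easy, discreet or good, or the man agrees, is confident or says yes. Only the awareness claim is an absolute whose second-best answer is a matter of degree.

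For these endpoints the worded claim is what the study delivers, and this is the only wording the plan gives for this one. A pass could license a statement that the data contradict.

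**Working it through.** The plan gives no success count or power for this item, so there is no figure to reproduce. The operating rule follows from its inputs.

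**Inputs.** n = 20 (section 9.2); null proportion 0.50, two-sided 5% level, 95% limits (section 9.1); lower limit above 50% to pass (sections 9.1 and 9.4). The plan does not name the interval. I use Clopper-Pearson, which matches the exact test.

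**Formulas.** For x successes out of n, the lower limit is the 2.5% quantile of Beta(x, n − x + 1) and the upper limit is the 97.5% quantile of Beta(x + 1, n − x). The chance of passing is P(X ≥ 15) for X binomial with n = 20 and success rate p.

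**Step 1: the threshold.**
- 15/20 = 75%: 50.9% to 91.3%, pass.
- 14/20 = 70%: lower limit 45.7%, fail.
- Under a true rate of 50%, P(X ≥ 15) = 21,700/1,048,576 = 0.0207, so the two-sided p-value at 15 is 0.041. This agrees with the interval rule.
- With 18 answers the threshold is 14 (lower limit 52.4%; 13/18 gives 46.5%). With 19, 17 and 16 answers it is 15, 13 and 13.

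**Step 2: what a pass implies about no awareness.** Hold the pooled count at 15 of 20, so the claim passes in every row, and vary the split.

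| Second-best answer | Top answer | No-awareness rate | Exact 95% CI |
|---|---|---|---|
| 15 | 0 | 0% | 0% to 16.8% |
| 10 | 5 | 25% | 8.7% to 49.1% |
| 9 | 6 | 30% | 11.9% to 54.3% |
| 0 | 15 | 75% | 50.9% to 91.3% |

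The first row is a logical extreme; its upper limit is 1 − 0.025^(1/20) = 16.8%. In the first two rows the claim passes while the whole interval for no awareness lies below 50%. From six top answers upwards the interval reaches past 50%, so the contradiction at the 95% level ends there. Only at 15 or more top answers do the same data also meet the rule for the literal claim.

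**Step 3: what a strict definition would cost.** If only the top answer counted, 15 of 20 men would have to give it. The documents contain no expected answer distribution, so these rates are assumptions. With 80% in the top two answers, the planned rule passes with probability P(X ≥ 15; p = 0.80) = 0.804, whatever the split. The strict rule passes with these probabilities:
- 60% choose the top answer: 0.126
- 50%: 0.0207
- 40%: 0.0016
- 20%: 1.8 × 10⁻⁷

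**The case against.** The strongest reply is about weight. This is one of 22 endpoints (17 five-point and 5 yes/no) in an exploratory proof-of-concept study with no formal hypothesis and no power. The phrase in Table 2 is an endpoint label, and the text of any eventual commercial claim is not in the documents. Section 9.1 reports discrete variables by number and percentage, so a reader may see the split between the two answers anyway. The 10 and 5 example is also the last split at 15 successes whose interval stays below 50%.

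Much of this is fair and limits the size of the point. A pass is not always wrong: with 15 or more top answers it would support the literal wording. No safety result or primary conclusion changes. But the descriptive split does not enter the pass decision, and the label is the only statement of what a pass is in favour of. If the label is meant as shorthand for low awareness, renaming it gives up only a wording that the rule does not test.

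**Conclusion.** The concern holds. Followed exactly, the plan can pass a no-awareness claim on data whose no-awareness rate lies below its own 50% bar: at 15 of 20 successes this happens whenever five or fewer men give the top answer. What a pass supports is low or no awareness in more than half of users.

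The conclusion rests on the plain meaning of the second-best answer and on Clopper-Pearson limits. The splits are illustrations, because the documents do not say how answers are expected to fall. The effect is confined to one exploratory secondary item. It should be corrected because supporting claims is the stated secondary objective.

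**What to change.** Keep the top-two rule and rename the endpoint and claim in Table 2 to *low product awareness during wear*. Add one sentence to section 9.1: for the awareness item, the proportion giving the top answer alone is also reported with its exact 95% confidence limits. Data, test and threshold stay as they are. The price is a weaker claim.

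If the sponsor wants to keep the no-awareness wording, success for this item should be the top answer alone, with that exception written into section 9.1. As Step 3 shows, this is costly at n = 20.

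Either route is an amendment. Section 11 states: "Example of significant change: Changes of inclusion criteria, end points or assessment methods". The change therefore needs agreement between sponsor and principal investigator, a justification, a new version number and date, a Change Log entry, and notification to or approval by the ethics committee and regulatory authorities. It must be made before database lock, and preferably before anyone has seen answers to this item. The study is open-label and section 8.1 allows real-time data review, so a choice between the two wordings made later could be driven by the results.
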